Evaluation of Pilot Online Binge Eating Disorder Group Intervention in under 18s.

Short Title: **Evaluation of Pilot Online Binge Eating Disorder Group in under 18s.**

Research Protocol Version 2.1 31/03/2023

IRAS Number

320293

Research Question

Can the guided self-help protocol be delivered as an online group intervention?

Core Research Group

[name], Coventry Warwickshire NHS Partnership Trust and Newman University (Chief Investigator; **email: [contact]**)

[name] [name], Newman University (Study Manager; **email: [contact]**)

[name], Coventry and Warwickshire Partnership NHS Trust

[name], Coventry and Warwickshire Partnership NHS Trust

[name], Coventry and Warwickshire Partnership NHS Trust

[name], Coventry and Warwickshire Partnership NHS Trust

Stakeholders

The following stakeholder groups have been identified:

- RISE Eating Disorder service users (current) who are diagnosed with a Binge Eating Disorder
- RISE Clinicians (including Psychologists, Cognitive Behavioural Therapy Therapists, Dieticians, and Assistant Psychologists)
- Non-client-facing service providers such as Service Managers and Commissioners/members of Clinical Commissioning Groups

Funding

This piece of research is being supported by the RISE Eating Disorder service at Coventry & Warwickshire Partnership NHS Trust and is not externally funded.

Sponsor

Coventry Warwickshire Partnership NHS Trust

Timeline

Start Date: 1st February 2023

Duration: 6 months

Background and Rationale

The National Institute for Health and Care Excellence (NICE) Guidelines (2017) recommend cognitive behavioural therapy (CBT) group therapy as an intervention for Binge Eating Disorders (BEDs). These guidelines do not differentiate between what is offered to adults and what is offered to under 18s for BED. Downey (2014) identified that there is limited research on group interventions for Binge Eating Disorder. Further, BED was only established as a diagnosis in the Diagnostic and Statistical Manual of Mental Disorders 5th Edition (American Psychiatric Association, 2013; DSM-5), which means that research is still in the early stages (Kober & Boswell, 2017).

Malhotra & Baker (2019) highlight that group therapy is an effective method of treatment for a variety of psychiatric and behavioural disorders. They found that it affects patients positively through the Yalom Therapeutic Factors (Yalom & Leszcz, 2020). For example, patients realising that there are others similar to them, improving their self-concept by assisting others and witnessing the success of other group members allows them to envision themselves also succeeding have all been shown to be beneficial. Rørtveit et al. (2021) found that a group program was thought to be an essential part of treatment. Jones (2019) also found that a CBT group intervention showed improvements for the participants and helped them regain control of their eating. Yu et al (2021) compared an online BEG group intervention to a face-to-face group amongst adults and found that the online option was feasible and effective. These studies were undertaken within the adult BED population and no paper was found evaluating the effectiveness or feasibility of a group intervention for under 18s.

Within RISE Eating Disorders Service, based in Coventry and Warwickshire Partnership NHS Trust (CWPT) individuals diagnosed with BED are offered guided CBT self-help based on the book Overcoming Binge Eating by Christopher Fairburn (2013). Due to the growing evidence that group therapy can be beneficial for adults with BED, we aim to explore whether or not this is also effective in under 18s. The large geographical area that the CWPT RISE service covers led us to developing the intervention for online use with the aim of increasing attendance and continued participation. The protocol for this BED group intervention has been developed using the current format for individual interventions based on Christopher Fairburn's book as a guide. The benefits of the research are that people on a waiting list will be offered treatment earlier.

Aims

The aim of our study is to assess whether the group intervention can be delivered per the protocol and obtain feedback from the participants of any recommended amendments/adaptations.

Methods

This research will:

1. Review individuals on the RISE Eating Disorder treatment waiting list for Binge Eating Disorder to assess their suitability for an online group intervention. Individuals will be reviewed in order on the waiting list.
2. A carer information session will be held online to discuss their role throughout the research.
3. An online one hour group intervention will be delivered once a week for 10 weeks.
4. Follow-up questionnaires will be distributed to carers 1 month after completion of group.

Participants

Individuals on the RISE Eating Disorders Treatment Waiting List will be reviewed by the RISE clinicians who will be facilitating the group intervention for suitability.

Inclusion criteria

- Diagnosed with Binge Eating Disorder
- Under 18 prior to the group starting
- Speaks English

Exclusion criteria

- If underweight
- If have a serious physical illness
- If pregnant
- Physical Health problems due to eating problem
- If mental health needs to be stabilised
- If significant problem with alcohol, drugs, or repeated self-harm
- Not in a place to start (changes upcoming or ongoing)

Procedure

Individuals from the treatment waiting list meeting the inclusion criteria will be approached by CWPT RISE study team clinicians to ask if they are interested in taking part in the research study. Those who express interest will be offered a face-to-face review appointment with two clinicians, including the chief investigator. If, from the review, it is felt that it is appropriate to offer them the study group intervention, it will be explained to them in detail and they will be handed a Patient Information Sheet (PIS), one for themselves and one for their parent / carer. They will be given a week to decide whether or not they would like to take part in the study after which time a clinician will contact them via telephone to ask them what they have decided and to answer any questions. The chief investigator will ensure that the individual is truly interested in the approach and that there is no coercion. Consent forms will be sent via email, which they will be asked to send back signed electronically and send back via email. Once the individual and their parents/carers have signed the consent forms, the parent /carer will be invited to attend an introductory information session online. This session will explain the principles of the group and how they can support the young person throughout the course of the group. Baseline questionnaires will be completed pre-intervention.

Group intervention

The BEG intervention protocol is a separate attached document. The outline of the group consists of:

- Error! Reference source not found.
- Error! Reference source not found.)
- Error! Reference source not found.
- Error! Reference source not found.
- Error! Reference source not found.

Upon completion of the group, the participants will be asked to complete the questionnaires again.

Participants will undertake a follow-up appointment face-to-face or online at one month post research intervention to complete the questionnaires again and to assess whether or not they continue to require RISE Eating Disorder Service support. If further support is required from the RISE Eating Disorders service, this will be offered by the team. If a need is identified for support that is not offered by the RISE Eating Disorder service, they will be signposted and/or referred to the appropriate service. If they no longer require treatment and are able to manage their binges, they will then be discharged from the service.

Measures

Questionnaires will be completed at baseline (pre-intervention), at completion of group and at one month post-intervention. Individuals will also be provided with an online feedback form at the end of the last group session to complete anonymously to assess their experience of the group.

The questionnaires used are: Eating Disorder Examination – Questionnaire (EDE-Q), Revised Children's Anxiety and Depression Scale (RCADS) Child and RCADS Parent. These are the standard questionnaires used within the service to monitor eating behaviours and mood. The EDE-Q was chosen over a specific binge eating one as this allows to monitor if the eating behaviours change to a different type of eating behaviour as it measures restriction and binging.

The results will be analysed quantitatively with repeated measures statistical tests. We are looking for the EDE-Q scores to reduce which would suggest a reduction in symptoms. Furthermore, we are monitoring mood through the RCADS to see if there is any change in their mood following the treatment.

The feedback form will be utilised qualitatively via content analysis to highlight any changes that the participants would suggest to the group and the space to express verbally how they experienced the group.

Anticipated impact and dissemination

If effective, the group intervention will be offered as a treatment option to service users from the RISE Eating Disorder Service going forward. The results will be disseminated through scientific papers and conferences. If the intervention is successful it might encourage services from other organisations to adopt this approach.

Ethics/regulatory approvals

Declaration of Helsinki

The Chief Investigator will ensure that this study is conducted in accordance with the principles of the Declaration of Helsinki.

Guidelines for Good Clinical Practice

The Chief Investigator will ensure that this study is conducted in full conformity with relevant regulations and with the ICH Guidelines for Good Clinical Practice (CPMP/ICH/135/95) July 1996.

Approvals

The research protocol, intervention protocol, informed consent forms, and participant / carer information sheets will be submitted to the Health Research Authority (HRA) and the CWPT R&D office for local approval.

The Chief Investigator will submit and, where necessary, obtain approval from the above parties for all substantial amendments to the original approved documents.

Data monitoring

The study may be monitored or audited for compliance with the Department of Health Research Governance Framework for Health and Social Care 2005.

Patient confidentiality

Study participants will be assigned a unique study identifier on recruitment. All data collected thereafter will be assigned to this study identifier. The study staff will ensure that the participants' anonymity is maintained. All documents will be stored securely and only accessible by study staff and authorised personnel. The study will comply with the Data Protection Act.

Ethical Considerations

Protecting patients' dignity is a critical part of this study. Study procedures, data handling and storage have been scrutinized to ensure that any privacy issues are mitigated.

All data will be kept strictly confidential.

Patient and Public Involvement

Service user involvement was sought. Feedback was positive in regards to the group and structure and recommendations have been taken into consideration.

End of study

End of study will be when all data has been collected, analysed and an end of study report produced.

Long term storage

All data will be kept electronically password protected. Only person who has access is the Chief Investigator. This will be archived for 5 years and destroyed following this.

References

Allen, K. L., Mountford, V., Brown, A., Richards, K., Grant, N., Austin, A., Glennon, D., & Schmidt, U. (2020). First episode rapid early intervention for eating disorders (FREED): From research to routine clinical practice. *Early Intervention in Psychiatry*, 14(5), 625–630.

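### The study asks whether the online group can be delivered as planned, but this protocol names no record of sessions, manual content or attendance as an outcome

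*Protocol*

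**What the plan says.** The Protocol poses a single Research Question: "Can the guided self-help protocol be delivered as an online group intervention". The Aims section has two halves, delivery and feedback: "The aim of our study is to assess whether the group intervention can be delivered per the protocol and obtain feedback from the participants". Methods gives the one countable delivery target: "An online one hour group intervention will be delivered once a week for 10 weeks".

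Background and Rationale presents feasibility as part of the gap in the literature: "no paper was found evaluating the effectiveness or feasibility of a group intervention for under 18s". It also gives the reason for going online: "with the aim of increasing attendance and continued participation". The same section adds an effectiveness purpose: "we aim to explore whether or not this is also effective in under 18s".

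Measures then lists the EDE-Q, RCADS Child and RCADS Parent at baseline, at the end of the group and one month later, plus one anonymous online feedback form given at the close of the last session. Scores are to be analysed with repeated-measures tests, and the form by content analysis. The session-by-session manual is a separate attachment and is not shown.

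**The concern.** The outcomes listed in Measures answer a different question from the one the study asks. Questionnaire scores bear on symptoms and mood, and the feedback form bears on experience and suggested changes. Neither says how many sessions took place, whether the manual's content was covered, or how many sessions each young person attended.

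Symptom change cannot stand in for delivery. EDE-Q scores could fall in someone who attended few sessions and stay flat in someone who attended all 10. If Measures is followed as written, the report will contain scores and comments, and this document designates nothing to report on delivery. A service considering the same format would want to know what was delivered and attended. Content covered in each session is also hard to reconstruct if nobody notes it at the time.

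**Working it through.** The Protocol gives no sample size, power or feasibility threshold, so there is no figure to reproduce. The check matches each part of the stated aim to each item in Measures.

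| Item in Measures | Stated use | Sessions, content or attendance? | Feedback? |
|---|---|---|---|
| EDE-Q | eating behaviours | no | no |
| RCADS Child | mood | no | no |
| RCADS Parent | mood | no | no |
| Feedback form | experience, suggested changes | no | yes |

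1. Instruments: 3 symptom or mood + 1 experience = 4. Instruments recording delivery: 0 of 4.
2. Analyses: repeated-measures tests on scores and content analysis of the form = 2. Analyses of delivery: 0 of 2.
3. Halves of the aim with a named instrument: 1 of 2 (feedback).
4. Search of the rest of the Protocol: attendance and continued participation appear only in Background and Rationale, as the motive for the online format ("with the aim of increasing attendance and continued participation"). No measure is attached there or elsewhere.
5. What could be derived from the planned data: questionnaires fall due at three time points, and Patient confidentiality says data are held under a study identifier. Counting returns at the end of the group and at one month gives an approximate completion and retention count. A return does not show how many of the 10 sessions the person attended, nor what was covered in them.
6. The feedback form cannot fill that gap. It is anonymous, so it cannot be linked to a starter. It is handed out at the end of the last session, so it is likely to miss anyone who stopped earlier.

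These counts show where the gap lies. They do not measure its effect on any estimate.

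**The case against.** The strongest reply is that delivery per protocol most naturally refers to the separate intervention manual. The Approvals section lists that document in the same submission, and it is a likely place for a register or checklist. This stands as a limit on the claim. A reader might infer that the study will collect no delivery data at all, and the document does not support that. What it supports is that this Protocol designates no such record as an outcome.

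A second reply is that a statistical analysis plan may exist. Descriptive attendance and participant-flow tables are commonly left to such a plan, and their absence here is no fault. Choosing the outcome that answers the research question is different: it belongs in the protocol, and this one does choose its measures.

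A third is that retention is not wholly unmeasured. That is right, since questionnaire returns give a rough count. Comments on the form may also touch on how the format worked, though that does not measure what was delivered.

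A fourth is that in a small single-service pilot, routine notes would probably yield sessions held and attendance. That is an assumption, and it is weaker for content covered.

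Two further inferences are tempting. One comes from the dates, "Research Protocol Version 2.1 31/03/2023" against "Start Date: 1st February 2023", a gap of 28 + 30 = 58 days: that a group is already running. The start date is the study's, not the first session's. Approvals in this same version still speaks of submission in the future, and review, consent and a carer session all come before the group. The other is that the dissemination section makes adoption depend on a test of effectiveness. It is a statement of intent with no criterion, and the point here does not rest on it.

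**Conclusion.** The point holds in a limited form. The Research Question and the first half of the Aims concern delivery, and this document names no record of sessions delivered, manual content covered or attendance as a study outcome. In size, this is one of the two halves of the aim and the whole of the only Research Question, with 0 of 4 instruments and 0 of 2 analyses directed at it.

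This is more than missing detail, because following the stated measures answers another question, and attendance per starter and content covered cannot be recovered from those instruments. The conclusion rests on this Protocol alone. If the manual already holds session and attendance records, what remains is that Measures does not name them. The symptom questionnaires still serve the effectiveness interest stated in Background and Rationale. Delivery records would not show whether the group works, since no comparator is described.

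**What to change.** In Measures, name deliverability as the outcome that answers the Research Question, made up of:

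- (a) sessions delivered out of 10, with a short facilitator tick-list of manual content covered in each; and
- (b) sessions attended by each starter, kept against the study identifier already assigned.

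The team should state in advance what it will count as delivery per protocol for (a) and (b). The Protocol gives no figures from which to derive a threshold, so none is suggested here. Describe change in EDE-Q and RCADS as exploratory alongside this outcome. If the manual already contains these records, name them in Measures instead of adding new ones.

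The cost is a small amount of record-keeping by facilitators who are present anyway, and a protocol amendment that may need approval from the bodies listed under Approvals. It needs no extra participants or visits.

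### Does the parent-rated RCADS lose its end-of-group assessment because the Procedure names only participants at that time?

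*Protocol*

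**What the plan says.** The schedule is set under Measures: "Questionnaires will be completed at baseline (pre-intervention), at completion of group and at one month post-intervention". The instruments named there are the EDE-Q and the two versions of the RCADS: "Anxiety and Depression Scale (RCADS) Child and RCADS Parent". No instrument has a different timetable. The planned analysis is stated in the same section: "The results will be analysed quantitatively with repeated measures statistical tests".

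Four other sentences touch on the same assessments:

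- **Procedure, baseline:** "Baseline questionnaires will be completed pre-intervention". No respondent is named.
- **Group intervention, end of group:** "Upon completion of the group, the participants will be asked to complete the questionnaires again". Participants are named and carers are not.
- **Group intervention, follow-up:** "Participants will undertake a follow-up appointment face-to-face or online at one month post research intervention to complete the questionnaires again". Again only participants are named.
- **Methods, item 4:** "Follow-up questionnaires will be distributed to carers 1 month after completion of group". Only carers are named, and only at one month.

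**The concern.** Two things look wrong. The two one-month sentences point to different people, carers in one and young people in the other. And at end of group the only instruction is addressed to participants. The Participants section describes these as young people from the waiting list, and the protocol mentions parents and carers separately where it gives them a task.

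If staff worked from the step-by-step text alone, the parent-rated RCADS might not be sent out when the group ends. A rating for that moment cannot be collected later. The parent-rated series would fall from three times to two, and the parents' view of change from baseline to the end of treatment would be lost. The protocol uses the RCADS to look for a change in mood after treatment, so this would remove one of the two informants at the first post-treatment assessment.

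**Working it through.** There is no stated figure to reproduce. The check is a count of instrument-by-time cells, with the passages set side by side.

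**Inputs.** Instruments (Measures): EDE-Q, RCADS Child, RCADS Parent, so 3. Times (Measures): baseline, end of group, one month, so 3. Cells: 3 × 3 = 9.

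| Time | Named in the step-by-step text | Required by Measures |
|---|---|---|
| Baseline | nobody (Procedure) | all 3 forms |
| End of group | participants (Group intervention) | all 3 forms |
| One month | participants (Group intervention); carers (Methods item 4) | all 3 forms |

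**Reading 1: the document as a whole.** Measures requires each form at each time. The EDE-Q and RCADS Child go to the young person, and RCADS Parent goes to a parent or carer, as its name says. Covered: 3 + 3 + 3 = 9 of 9. Open: 0.

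**Reading 2: participants taken to mean participants only at end of group, with baseline assumed complete.** Baseline 3, end of group 2, one month 3 (young people for two forms, carers for the third through Methods item 4). Covered: 3 + 2 + 3 = 8 of 9. Open: 1. RCADS Parent has 3 pairwise time comparisons (three times taken two at a time). Two of them use end of group, so 3 − 2 = 1 would remain, baseline to one month.

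**Reading 3: a cell counts only if the step-by-step text names its respondent.** Baseline 0, end of group 2, one month 3. Covered: 0 + 2 + 3 = 5 of 9. Open: 4, including the baseline EDE-Q. Nobody would accept that result. It shows that these sentences were not written as a full list of respondents and must be read with Measures.

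**Choosing between Readings 1 and 2.** Three points in the text favour Reading 1.

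1. Reading 2 relies on Measures to fill the unnamed baseline cell and then sets Measures aside at end of group, although one sentence in Measures covers both times.
2. The end-of-group and follow-up sentences both say the questionnaires are completed again, which points back to the baseline set. If that set contains RCADS Parent, so does the repeat. Taken word for word, young people would be filling in a parent form, so participants must be shorthand for the family's set of forms.
3. Methods items 1 to 4 are an outline. They contain no baseline or end-of-group questionnaire step at all, so the absence of carers at end of group there carries no information. Item 4 also speaks of distributing forms, while the follow-up text speaks of completing them. Both can hold at one month.

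**The case for a change.** The strongest opposing case is that this is data collection and not analysis. A statistical analysis plan would not tell staff to contact carers, and no analysis can restore a rating that was never taken. The protocol gives carers their own mention at the information session, the information sheet, consent and the introductory session, so their absence at end of group could be a real omission and not shorthand. Naming the respondents would cost a few words and one message per carer.

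Much of this stands. The wording is loose, the protocol does usually distinguish carers from participants, and a missed end-of-group rating would be permanent. What does not follow is that the form would be missed. The end-of-group sentence does not exclude carers, and the section that sets the schedule requires the form at that time. Measures also describes these instruments as the service's routine ones, so the clinicians running the group already know which form goes to the parent. Carers are briefed on their part at an information session before the group begins, and their information sheets and the separate intervention protocol are not at hand, so the absence of an instruction can be asserted only for this document.

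Even if the cell were lost, the protocol does not commit to a three-time analysis of the parent form. Repeated-measures tests can be run on two times, and the child RCADS would still cover all three.

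**Conclusion.** No change to the plan is needed. The sentences differ in whom they name, but they do not conflict once read with Measures, and following the protocol as a whole yields all 9 cells. The possible loss runs from 0 to 1 of 9 cells, with 0 the better-supported figure. The upper end requires staff to treat the end-of-group sentence as overriding Measures, while still relying on Measures at baseline.

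This rests on three assumptions: that Measures is the governing schedule, that RCADS Parent is completed by a parent or carer, and that staff handle the service's usual forms in the usual way. The main aim, which is delivery of the group as designed and participants' feedback, does not depend on the parent-rated RCADS in any case. Naming the respondent at each time would record what staff would do anyway and would add no data.

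### The only named feedback form is tied to the close of the tenth weekly session, and the protocol makes no provision for feedback from participants who stopped earlier or missed that session

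*Protocol*

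**What the plan says.** The Research Question of the Protocol is "Can the guided self-help protocol be delivered as an online group intervention". The Aims section sets two tasks: to assess whether the group can be delivered per protocol, and to "obtain feedback from the participants of any recommended amendments/adaptations". Background and Rationale explains that the online format was developed "with the aim of increasing attendance and continued participation".

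The schedule is in Methods: "An online one hour group intervention will be delivered once a week for 10 weeks". The feedback instrument is in Measures: "Individuals will also be provided with an online feedback form at the end of the last group session to complete anonymously". Measures then gives its use. It is to be examined by content analysis for "any changes that the participants would suggest to the group and the space to express verbally how they experienced the group".

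Measures lists the questionnaires separately: the EDE-Q and the child and parent versions of the RCADS. These are completed at baseline, at completion and one month later. The purpose of the one-month appointment, described under Group intervention, is "to complete the questionnaires again and to assess whether or not they continue to require RISE Eating Disorder Service support". For the content of the group the reader is referred elsewhere: "The BEG intervention protocol is a separate attached document".

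**The concern.** A form issued as the final session closes most naturally reaches the people in that session. Participants who have stopped attending are the ones best placed to say what made the format hard to continue with and what they would change. The online format was chosen partly to keep people attending, so their views bear directly on whether the group can be delivered this way.

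If they are not asked, a content analysis meant to find recommended amendments can miss whole themes. An analysis plan cannot repair this later, because feedback that was never requested is not in the data. The Protocol also foresees offering the group routinely, and adoption by other services, if it works. A gap in the suggestions could therefore carry forward into the version that is rolled out.

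**Working it through.** The Protocol states no figure on this point, so this is a check of the text. The one derivation is 1 session per week × 10 weeks = 10 sessions, so the last session is session 10 of 10.

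1. **When is the form given?** Measures names one time only, the close of session 10. No second occasion is given.

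2. **Is it repeated with the questionnaires?** No. Measures defines the questionnaires as the EDE-Q and the two RCADS versions and introduces the feedback form separately. The repeat assessments at completion and at one month therefore do not include it.

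3. **Does the one-month appointment collect feedback?** Its listed purposes are the questionnaires and the need for further service support. Feedback on the group is not among them. The follow-up step in Methods likewise mentions only questionnaires, sent to carers.

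4. **Is there a separate verbal route?** The words about expressing experience verbally stand in the same sentence as the content analysis of the form. They set no other time, contact or interviewer.

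5. **Does patient and public involvement fill the gap?** That section reports service-user input in the past tense, as already obtained and considered. It is not a plan to collect the views of participants in this study.

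6. **Is early stopping mentioned anywhere?** No section of this document deals with missed sessions, stopping attendance or withdrawal.

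7. **Who are the recipients?** The sentence in Measures says only that individuals receive the form. Two procedures fit it. In one, the form goes to every participant on the date of the last session. In the other, it is issued within that session to those present. The text does not choose between them. Under the first, all starters are reached. Under the second, everyone absent from session 10 is missed, whether they left for good or missed one week.

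Steps 1 to 6 show that nothing else in the document settles step 7.

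**The case against.** The strongest case against is that the document is silent here rather than wrong. The word used for recipients carries no attendance condition, the form is online, and the study already emails consent forms to families, so sending it to everyone is at least as natural a reading. The intervention protocol and the information sheets are not at hand and may describe distribution. Asking at the end, when the whole programme has been seen, is also a sound choice of timing. All of this stands. It keeps the point small and limits it to this document.

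It does not remove the point. Feedback is part of the aim, its one named instrument is anchored to a session rather than to a list of people, and following the text as written can yield suggestions only from those still attending. An item on obstacles to attendance would add information even if the sponsor already means to send the form to everyone.

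Three stronger readings are tempting, and the documents support none of them:

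- **Early leavers are excluded.** A reader might infer this from the timing, but the wording does not say so.
- **Anonymity means the recipients have to be fixed in advance, because replies cannot be matched to attendance.** This goes too far. An anonymous form can ask how many sessions the respondent attended. Patient confidentiality also assigns all data collected after recruitment to a study identifier, which leaves it unclear how unlinkable the replies are.
- **The feedback will be too favourable, or a given share of views will be lost.** Nothing in the document gives a direction of bias, a group size or a drop-out rate. Any percentage would come wholly from assumption, and a count of absentees from session 10 would mix one-off absence with stopping.

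**Conclusion.** The point holds in limited form. The Protocol ties its only clearly named feedback instrument to the close of session 10 and makes no provision, in this document, for participants who stopped earlier or missed that session. If the form is distributed in that session, the content analysis serving the feedback aim rests on those still attending and can miss reasons for stopping.

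This is conditional on the in-session reading and on the unseen intervention protocol and information sheets not providing otherwise. The size cannot be given from the documents. What is at risk is missed themes in a qualitative analysis; the questionnaire results are not affected. It is a cheap improvement of low severity.

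**What to change.** In Measures, state that the anonymous online form is sent at the scheduled end of the group to every participant who attended at least one session and has not withdrawn consent to research contact. Add one optional item, shown to all respondents, on roughly how many sessions they attended and what made attendance hard or led them to stop. Report the numbers of forms sent and returned.

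The cost is one sentence, one form item and one message per participant. The downsides are:

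- Some leavers will not reply, so the gap narrows but may not close.
- Early leavers recall over a longer interval. With weekly sessions, someone whose last session was number k is asked 10 − k weeks later: 6 weeks for k = 4, and 9 weeks for k = 1.
- In a small group, an answer about stopping may identify its author, which is why the item should be optional.
- An amendment may be needed. Whether it counts as substantial under Approvals is for the chief investigator and the approving bodies to judge.

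People who consented but attended no session fall outside this change, because the form asks about experience of the group.
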